9.2.6.3 Provision of Care for Subjects after Trial Discontinuation

The investigator is responsible for ensuring the adequate and safe medical care of subjects during the trial. At the end of the trial or after subject discontinuation, the investigator will ensure that appropriate consideration is given to a subject's after-trial care. Subjects will be treated by their physician according to their medical condition and standard treatments in China. Additionally, the sponsor will follow all applicable local or international regulations and guidelines regarding follow-up care for subjects.

9.2.7 Suspension or Premature Termination of an Investigative Site

Trial participation by individual sites may be suspended or prematurely terminated by the sponsor. Reasons for the suspension or premature termination of sites include, but are not limited to, the following:

- Investigator request;
- Serious or persistent noncompliance with the protocol, local regulations, and/or Chinese GCP;
- Suspicion of fraud;
- Failure to accrue subjects at an acceptable rate; and/or
- Ethical issues.

The sponsor will provide the investigative site with written notification documenting the reason for suspension or premature termination. The sponsor will inform the responsible regulatory authority, as appropriate, and ensure the IEC/IRB is notified. If the suspension or premature termination was in the interest of safety, the sponsor will inform all other principal investigators.

In cases of temporary suspension at an investigative site, the sponsor will conduct an analysis of the reason(s) for suspension. After completing this analysis and implementing necessary corrective actions, a temporary site suspension may be lifted. The sponsor will inform the principal investigators, the IEC/IRB, and, where appropriate, the regulatory authority of the rationale, providing relevant data supporting this decision. Concurrence must be obtained from the IEC/IRB and, where appropriate, regulatory authorities before the investigative site resumes trial activities. If subjects were informed of the suspension, the principal investigator or authorized designee will inform them of the reasons for resumption.

In cases of premature termination, the investigator will conduct site-closure activities in accordance with all applicable sponsor, local, and international guidelines and regulations.

9.2.8 Suspension or Premature Termination of the Trial

Should the investigator, sponsor, the NMPA, or local regulatory authorities become aware of conditions arising during the conduct of this trial that may warrant the cessation of the trial, such action may be taken. Prior to such action, consultation between the sponsor, the investigator, and, as appropriate, the NMPA and/or local regulatory authorities will occur.

Reasons for the suspension or premature termination of the trial include, but are not limited to, the following:

- Anticipated benefit cannot justify the risk;
- New scientific data do not justify a continuation of the trial;
- Determination of a potential safety risk to subjects;

- Inadequate subject enrollment;
- Decision by the regulatory authority or IEC/IRB to suspend or terminate approval/favorable opinion for the trial; and/or
- Sponsor decision.

If suspicion of an unacceptable risk to subjects arises during the trial or if instructed by the IEC/IRB or regulatory authorities, the sponsor will suspend the trial while the risk is assessed. If the analysis determines that implementing necessary corrective actions is sufficient, a temporary trial suspension may be lifted. If an unacceptable risk is confirmed, the sponsor will terminate the trial.

If the trial is suspended or prematurely terminated for any reason, the sponsor will inform all investigators and relevant regulatory authorities promptly of the trial suspension/termination and reason for the action, as detailed in Section 9.2.7. The investigator will conduct site-closure activities in accordance with all applicable sponsor and local/international guidelines and regulations.

9.2.9 End of Trial

The end of the trial is defined as when the last subject completes the last visit.

10 TRIAL DEVICE AND TREATMENT OF SUBJECTS

10.1 Description of Trial Device

The Ulthera DeepSEE System is intended for lifting and sculpting of skin through deposition of ultrasound energy at depths between 1.5 and 4.5 mm beneath the skin surface. In the current study, the intended use of the Ulthera DeepSEE System is for improvement in skin laxity of the lower face and submentum.

The Ulthera DeepSEE System integrates the capabilities of ultrasound imaging with those of MFU therapy. The imaging feature, using the DeepSEE transducer, allows the user to visualize the dermal and subdermal regions of interest before treatment. This imaging feature enables users to ensure proper transducer coupling with the skin and adequate delivery of treatment energy at desired depths, avoiding structures such as bone.

The therapy feature directs highly focused, low energy (< 3 J) ultrasound waves to a specific tissue depth (mid to deep reticular dermis and sub-dermis) in the treatment area, sparing deeper tissues and the overlying epidermis. This controlled deposition of ultrasound energy heats the tissue and produces a line of discretely-spaced, thermal coagulation points (TCPs) at a specific treatment depth. This line of TCPs is also known as a treatment line. The end effect of the produced TCPs is the initiation of a tissue healing response (i.e., increased collagen and elastin synthesis), producing lift and tightening of skin.

A diagram of the Ulthera DeepSEE System is provided in Figure 1, consisting of three primary components: the control unit, the transducer, and the handpiece.

For this trial, the Ulthera DeepSEE System will be supplied by Ulthera, Inc. (Mesa, Arizona, USA) and marked for trial-specific clinical use. The sponsor will also provide a cart on which the Ulthera DeepSEE System will be placed, complete with drawers for storage of the transducers.

10.3 Methods of Assigning Subjects to Trial Groups

Subjects who complete all screening assessments and meet all eligibility criteria will be enrolled and randomized 1:1 to one of the following groups:

- Treatment Group: Treatment with the Ulthera DeepSEE System at Day 1; or
- Control Group: Untreated control, with delayed treatment at Day 90.

Trial group assignments will be made based on the trial randomization scheme. A randomization list block-stratified by site will be created by a validated computerized randomization program. This randomization list will be uploaded to an electronic system that will allocate trial group assignment to the subjects in the eCRF according to the randomization list, if all relevant data were entered and the subject is eligible for participation in this trial. Randomized subjects will receive a unique randomization number, which will be recorded along with the date of randomization in the eCRF.

This information will remain in the subject's source documents and be made available for verification of the proper randomization sequence by the sponsor or designee during monitoring visits.

Additional details regarding randomization are provided in Section 13.2.

10.4 Blinding Procedures

10.4.1 Blinding

In this prospective trial, the treating investigators and subjects will not be blinded to trial treatment. For the primary effectiveness endpoint only (proportion of subjects with improvement in lower face and submental skin laxity; see Section 7.2.1.1), the blinded evaluators will be blinded to trial group assignment.

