7.2.1.2 Secondary Effectiveness Endpoints

- Displacement of skin (mm) in the submentum at Day 9
- Proportion of subjects with any improvement Investigator Global Aesthetic Improvement Scale (iGAIS) at Day 90

 , as assessed by the treating investigator for the Treatment Group.
- Proportion of subjects with any improvement
 Global Aesthetic Improvement Scale (sGAIS) at Day 90
 , as assessed by the subjects in the Treatment Group.
- Change from baseline in FACE-Q[™] Satisfaction with Lower Face and Jawline score (Rasch-transformed) at Day 90, as assessed by the subjects in the Treatment Group.

[figure not shown]

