10.4.2 Planned Unblinding

Planned unblinding procedures are not necessary in the current trial design, as the treating investigator, trial coordinator, sponsor staff, and other trial personnel are not blinded to trial group assignments.

[figure not shown]

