10.7 Trial Supplies and Packaging of Treatment Supplies

The sponsor will provide the Ulthera DeepSEE System including console, handpiece, and transducers. This investigational medical device (IMD) is to be used exclusively for treatment of subjects enrolled in this trial and will be labeled as follows: "CAUTION - Investigational Device. Limited to Investigational Use Only." Device labels will also note the sponsor name and address, manufacturer name and address, study number, the quantity within the package, and any other required information (if applicable).

Sites will also be supplied with trial-specific ultrasound gel, cleanser for washing of the treatment area, 3D facial camera system (Section 11.2.1.2), and a standardized hand mirror for use during the FACE-Q and sGAIS assessments. Clinical trial supply should be stored in a controlled area with limited access and stored separately from any commercial supplies.

The sponsor will package trial materials according to applicable regulatory requirements. The sponsor will provide all pertinent labeling information, as well as a description of the specific device-packaging conditions.

Parts of the trial device may be subject to reduced labeling according to the applicable regulations. Records about production date, serial number (as applicable), test record related to product quality, and records of transportation, maintenance, and delivery must be kept with the trial device.

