13.4.1.2 Secondary Effectiveness Endpoints

[figure not shown]
The secondary effectiveness endpoints are defined in Section 7.2.1.2.

Displacement in skin in the submentum at Day 90 will be analyzed by applying an ANOVA with fixed effects treatment group and site. The variance matrix among treatment groups will be left unspecified to allow for potential heterogeneous variances. Denominator degrees of freedom will be approximated by the Satterthwaite method. The ESTIMATE statement will be used for the statistical test and to provide point estimate and confidence interval for the difference Treatment – Control.

The other secondary effectiveness endpoints will be analyzed by descriptive statistics including confidence intervals (CIs). For the iGAIS and sGAIS assessments, the proportion of subjects in the Treatment Group with any improvement will be calculated and given as number of subjects with improvement/number of subjects in the corresponding analysis (n/N) and as percentage (%).

For the FACE-Q satisfaction with lower face and jawline, Rasch-transformed scores, ranging from 0 to 100, will be summarized for the Treatment Group using descriptive statistics. Higher scores reflect a better outcome. If missing data are less than 50% of the scale's items, the mean of the completed items will be inserted.

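### Stated blinding covers the primary endpoint only, so nothing in the readable plan protects the between-group test of submental displacement from knowledge of group

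*Protocol*

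**What the plan says.** Protocol 10.4.1 states that "the treating investigators and subjects will not be blinded to trial treatment". It then gives the scope of evaluator blinding: "For the primary effectiveness endpoint only", with a reference to Section 7.2.1.1. SAP 2.3 repeats that scope, in text broken by extraction. Protocol 10.4.2 explains why no planned unblinding is needed: the "treating investigator, trial coordinator, sponsor staff, and other trial personnel are not blinded to trial group assignments".

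Protocol 7.2.1.2 lists "Displacement of skin (mm) in the submentum" as a secondary effectiveness endpoint. Protocol 13.4.1.2 analyses it by an ANOVA with treatment group and site as fixed effects. For the Treatment minus Control difference it adds: "The ESTIMATE statement will be used for the statistical test", together with a point estimate and confidence interval. The remaining secondary effectiveness endpoints (iGAIS, sGAIS, FACE-Q) are assessed in the Treatment Group and summarised descriptively. In the readable text, displacement is therefore the only secondary effectiveness endpoint with a between-group test.

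SAP 6.1.2 derives displacement, per subject, as summaries of X, Y and Z vectors over all points. Protocol 10.7 supplies sites with a "3D facial camera system (Section 11.2.1.2"), but Sections 11.2.1.1 to 11.2.1.3 are not in the public text. SAP 6.4.4 states that only the primary endpoint has a confirmatory analysis.

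**The concern.** Subjects know their group and the control is untreated. In that setting a measurement in millimetres is likely to be read as objective support for the blinded primary result. That reading is sound only if the measurement cannot depend on group.

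If people align the images, choose the region that supplies the points, or reject poor images, each of these is a judgement that knowledge of group could tilt slightly. A small systematic tilt would appear in the ANOVA as a treatment effect. The analysis could not separate it from a real one, because it follows the randomised groups exactly.

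At stake is the credibility of one supportive endpoint, not the trial's criterion for success.

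**Working it through.** **1. Setting the provisions side by side**

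| Question | Primary endpoint | Submental displacement |
|---|---|---|
| Tested Treatment versus Control? | Yes (Protocol 13.4.1.1) | Yes (Protocol 13.4.1.2) |
| Evaluator blinding stated? | Yes (Protocol 10.4.1, SAP 2.3) | No; the stated scope is the primary endpoint only |
| Assessor or process visible? | Blinded evaluators | Not in the readable text |
| Confirmatory? | Yes (SAP 6.4.4) | No |

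Three states of affairs fit this text:

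- Displacement is processed by people who know the group.
- It is processed masked, and 10.4.1 describes the plan too narrowly.
- It is fully automated, and evaluator blinding matters little.

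The readable text does not decide among them. In each case a sentence in 10.4.1 and SAP 2.3 would settle the point.

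**2. The plan's own figure**

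The one sizing figure that can be checked is the number to screen (Protocol 9.1): 200 / (1 − 0.20) = 250, which reproduces. It has no bearing on blinding. The power calculation is not in the public text, and the documents give no SD or measurement error for displacement.

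**3. What an arm-related shift would do (illustration)**

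Inputs from the documents: 200 randomised 1:1, hence 200 / 2 = 100 per arm; two-sided test at 5% (Protocol 13.4). Assumptions: no true effect, a measurement shift of d SD between arms, equal variances and a normal approximation for a single test.

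The shift in the test statistic is δ = d / √(2/n). The chance of a significant result is P(Z > 1.96 − δ) + P(Z < −1.96 − δ).

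For n = 100, √(2/100) = 0.1414:

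- d = 0.1: δ = 0.707; 0.1051 + 0.0038 = 0.109
- d = 0.2: δ = 1.414; 0.2926 + 0.0004 = 0.293
- d = 0.3: δ = 2.121; 0.5641 + 0.0000 = 0.564

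| Assumed shift (SD) | 100 per arm | 80 per arm |
|---|---|---|
| 0 | 5.0% | 5.0% |
| 0.05 | 6.4% | 6.2% |
| 0.1 | 10.9% | 9.7% |
| 0.2 | 29.3% | 24.4% |
| 0.3 | 56.4% | 47.5% |

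The 80-per-arm column is an assumed allowance for missing images, since effectiveness analyses default to observed cases (Protocol 13.4.1). Masked or fully automated measurement corresponds to d = 0 for the processing step, which restores 5%.

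**The case against.** The strongest objection is that the sections where image capture and processing would be described are absent from the public text, and such an absence is not a gap in the plan. The SAP's version of the unblinding statement (2.4.1) also breaks just after its mention of other trial personnel, so an exception may have stood there. Summaries of vectors over all points are compatible with software output. No readable passage describes anyone aligning images, choosing an area or rejecting images. An area of interest appears in the abbreviation list, but its use is not visible and it could be a fixed region. The shifts of 0.05 to 0.3 SD are assumed, and the same table would fit any two-arm comparison of this size. Displacement is secondary, so a false positive cannot establish effectiveness.

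All of this stands, and it rules out a stronger reading that a reader might infer: that the displacement test rests on measurements made by people who know the group. No document says that. Even the image-based nature of the endpoint is inferred, from the camera and the X/Y/Z vectors.

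What the objection does not remove is the explicit wording of 10.4.1. Limiting blinding to the primary endpoint only is a positive statement of scope, not a redaction. Automation, if present, is nowhere stated in the readable text, and software output can still depend on which surface and which images are supplied to it.

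**Conclusion.** The point holds as a limited one. The plan expressly confines evaluator blinding to the primary endpoint while testing submental displacement between groups, and the readable text does not protect that measurement from knowledge of group. Bias is possible but not demonstrated. The figures of 10.9%, 29.3% and 56.4% show what arm-related shifts of 0.1, 0.2 and 0.3 SD would do at 100 per arm with no true effect. They do not show that such shifts are likely.

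It would also be wrong to infer that the trial's main conclusion is in doubt. The primary endpoint has blinded evaluators and is the only confirmatory analysis. The gain from acting is a more credible supportive endpoint, so this is a cheap improvement and not a correction on which the trial depends.

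**What to change.** Amend Protocol 10.4.1 and SAP 2.3 so that blinding also covers the processing of displacement, and align Protocol 10.4.2 and SAP 2.4.1 with that wording. Specifically:

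- Process baseline/Day 90 image pairs under a code that carries no group information.
- Keep the baseline/Day 90 order visible, because displacement is directional and needs a known reference image.
- Fix any area selection and any rejection of images for quality before the code is linked to group.
- If processing is fully automated, state that instead.

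The cost is a coding step at image transfer and short wording changes in the two documents. No extra reader is needed. One limitation remains: image capture at the site by unblinded staff would still be unmasked, and the amended text should say so.

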10.4.2 Planned Unblinding

Planned unblinding procedures are not necessary in the current trial design, as the treating investigator, trial coordinator, sponsor staff, and other trial personnel are not blinded to trial group assignments.

[figure not shown]
10.5 Trial Treatment

All protocol-specific criteria for the administration of trial treatment must be met and documented prior to administration of any trial treatment. All treatments with the Ulthera DeepSEE System will be performed onsite by the treating investigator; subjects will not be dispensed any investigational material. Any noncompliant investigative site may be discontinued from the trial (Section 9.2.7).

10.5.1 Planned Treatment Procedure and Administration

10.5.1.1 Pre-treatment Assessments

All subject-related, pre-treatment activities (Section 11.1) should be completed prior to administration of pre-treatment medications.

10.5.1.3 Treatment Regions and Treatment Administration Procedure

The skin of the midface, lower face, submentum (beneath the chin), and upper neck will be treated as described in Table 3 with three Ulthera DeepSEE transducers:

• DS 7-4.5: 7 MHz, 4.5 mm focal depth

DS 7-3.0: 7 MHz, 3.0 mm focal depth

DS 10-1.5: 10 MHz, 1.5 mm focal depth

All investigators will be trained by the sponsor to use the Ulthera DeepSEE System ultrasound imaging to ensure that proper treatment is delivered (e.g., transducer contact, depth).

For the mid and lower face, treatment lines should be administered starting with the DS 7-4.5 transducer, followed next by the DS 7-3.0 transducer, and then by the DS 10-1.5 transducer. For the submentum (underneath chin) and neck, treatment lines should be administered starting with the DS 7-3.0 transducer, followed next by the DS 10-1.5 transducer.

Overall, a total of 820 treatment lines are planned for administration. At the discretion of the treating investigator, subjects may receive up to 10% additional treatment lines, concordant with variations of individual subject anatomy such as increased surface area within the treatment region. However, the treating investigator should ensure that the additional treatment lines are delivered in a symmetrical fashion. For example, if additional treatment lines are delivered to the Right Mid/Lower Face region, approximately the same number of additional treatment lines should be delivered in the Left Mid/Lower Face region.

10.5.2 Selection and Timing of Treatment for Each Subject

Subjects in the Treatment Group will receive a single treatment with the Ulthera DeepSEE System at Day 1 (V2). Subjects in the Control Group will not receive treatment at Day 1 and will remain untreated until Day 90 (V3). Following completion of all protocol-mandated assessments at Day 90 (Section 11.1), the Control Group will receive a single treatment with the Ulthera DeepSEE System.

10.5.3 Treatment Interruption and Modification

If any problems occur during system operation, the treating investigator should take the following immediate action(s): lift the transducer off the subject's skin, press the **See** button on the handle to discontinue treatment in progress, and/or press the red emergency **Stop** button to completely halt system operation.

10.6 Prior and Concomitant Therapy

Medical history and concomitant therapy that is deemed relevant for study conduct by the investigator (e.g., chronic diseases, previous aesthetic treatments) should be documented in the eCRF. Restrictions regarding concomitant therapy are discussed in detail in Section 9.2.2 (Exclusion Criteria) and Section 9.2.3 (Restrictions during the Trial).

10.7 Trial Supplies and Packaging of Treatment Supplies

The sponsor will provide the Ulthera DeepSEE System including console, handpiece, and transducers. This investigational medical device (IMD) is to be used exclusively for treatment of subjects enrolled in this trial and will be labeled as follows: "CAUTION - Investigational Device. Limited to Investigational Use Only." Device labels will also note the sponsor name and address, manufacturer name and address, study number, the quantity within the package, and any other required information (if applicable).

Sites will also be supplied with trial-specific ultrasound gel, cleanser for washing of the treatment area, 3D facial camera system (Section 11.2.1.2), and a standardized hand mirror for use during the FACE-Q and sGAIS assessments. Clinical trial supply should be stored in a controlled area with limited access and stored separately from any commercial supplies.

The sponsor will package trial materials according to applicable regulatory requirements. The sponsor will provide all pertinent labeling information, as well as a description of the specific device-packaging conditions.

Parts of the trial device may be subject to reduced labeling according to the applicable regulations. Records about production date, serial number (as applicable), test record related to product quality, and records of transportation, maintenance, and delivery must be kept with the trial device.

